
5C1b) The attention control intervention is designed to provide general supportive cancer-related education that is not directly related to treating CRF. The following booklets published by the NCI will guide the delivery of planned, educational content, delivered weekly by the ACG nurse intervener as prescribed using the protocol in Appendix A3: 1) What You Need to Know About Lung Cancer; 2) Taking Time: Support for People with Cancer; and 3) Care for the Caregiver. The ACG participants will be matched to the IIG participants in the

Protocol Version 4.0 (7/19/2023). UNMC IRB 560-18 EP. Contact PI: [name] [name], RN.

exercise intervention in terms of frequency of visits (1 visit per wk); duration of visit (about 10 mins); and social interaction (one-on-one instruction from a nurse). Each booklet will be used over a 2-wk period with calls about 10 mins. Nurse and patient will be given copies of each NCI booklet and phone scripts for each visit (Appendix A3). Highlights of each booklet will be pointed out following the script. While there is a sentence recommending exercise as a way to treat fatigue, and discussion on general nutrition provided in the “Taking Time: Support for

People with Cancer” brochure, fatigue and general nutrition will not be reviewed in the ACG intervention. Reading this recommendation is equivalent to what many health care providers tell their patients to do providing a systematic suggestion while our intervention is being tested over and above this suggestion.

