5C2) Study Procedures. IIG participants will have baseline data collected by the nurse recruiter. Following principles of transitional care,¹²⁴ the exercise nurse intervener will engage the participant using protocol in Appendix A4 in the hospital post-surgery to review the exercise intervention and teach PSE-enhancing CRF self-management education (Appendix A5) that uses National Comprehensive Cancer Network Guidelines.¹²⁵ To ensure continuity, a primary nurse will be assigned to each participant. Data collectors will contact IIG by phone within approximately 24 hrs of discharge to collect data (if too ill, re-scheduled within approximately 3 days of discharge) and at approximately the end of each week for 6 wks. The nurse will make a phone visit within approximately 24 hrs of post-surgical discharge to screen participant’s readiness to start exercise. Participants will be deemed ready to start if usual level of severity for key symptoms of pain, nausea, and dyspnea are rated ≤ 4 on an 11-point scale (0-10, 10 = most severe). If participant is ready to exercise, a home visit will be scheduled to start exercise within approximately 4 days of discharge. When severity of a key symptom is rated > 4 , nurse will intervene and contact participant’s surgeon’s office for recommendations. The nurse will repeat this step each day until participant is ready to start exercising. Once participant is ready, nurse will arrange home visit within approximately 3 days. The initial home visit will include connecting Wii to participant’s TV, setting up Wii FitPlus log on password, teaching exercise intervention, and reinforcing CRF self-management education and exercise safety precautions. The nurse will follow-up with phone visit within approximately 24 hrs to answer questions and concerns, make a follow-up home visit at approximately the start of wk 2 of exercise, phone visits at approximately the start of wks 3-6, and additional visits per participant request. During visits, nurse will review IIG participant’s Daily Diary (Appendix A2) with participant and provide PSE-enhancing CRF self-management interventions (Appendix A6). These PSE-enhancing interventions include providing mastery and/or vicarious experiences; social encouragement; and reinterpretation of physical and psychological symptoms to support exercise program to adjust exercise prescription per guidelines. Participant uses Daily Diary to record weekly exercise activity and exercise-related symptoms or issues. IIG participants will be given the option to extend exercise for another 6 wks to study wk 12. Data collection will continue on a weekly basis, culminating with a 6MWT at end of approximately wk 12. Nurse calls will continue weekly to prescribe balance exercises and advance walking prescription 5 mins each week, with goal of achieving minimum 30 min/day. Participants may extend beyond 30 min/day with rate of increase no more than 5 min/day each wk, with participants’ PSE for attaining that duration $\geq 70\%$ on a 0-100% scale (100%=high PSE) (Appendix A1).

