
5C2a) WCG participants will have baseline data collected pre-surgery by the nurse recruiter and receive a pedometer and instructions for recording total steps/day in Daily Diary (Appendix A7). The WCG nurse intervener (nurse) will visit in the hospital post-surgery to review study trajectory. Research staff will contact WCG by phone within approximately 24 hrs of discharge to collect post-surgery data (if too ill, data collection rescheduled within 3 days of discharge). Research staff will perform phone visits using protocol in Appendix A8 at the approximate end of wks 1-6 to control for staff interaction and data collection. During wk 6, an exercise nurse intervener will make a phone visit to screen participant’s readiness to start intervention as described for IIG participants. Once participant is ready to start, nurse will arrange home visit within approximately 3 days. The exercise intervention and procedures will be identical to those received by the IIG group during wks 1-6. Staff contact WCG by phone (if too ill, data collection re-scheduled within approximately 3 days) to collect data at the end of approximately wks 7-12.

5C2b) ACG participants will have baseline data collected pre-surgery by a nurse recruiter and receive a pedometer and instructions for recording total steps/day in Daily Diary (Appendix A7). The ACG nurse intervener will visit in the hospital post-surgery to review study trajectory, make a phone visit within approximately 4 days of post-surgical discharge to initiate the ACG intervention (Appendix A3), and make phone visits at the start of approximately wks 2-6. During visits, the nurse will deliver the ACG intervention. Data collectors will contact ACG by phone within approximately 24 hrs of hospital discharge (if too ill, re-scheduled within approximately 3 days of discharge) and at the approximate end of each week for 6 wks to

obtain outcome measures.

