5C3) Protocol Fidelity. Protocol fidelity will ensure consistency in design, dose, training, delivery, receipt, and enactment of the intervention (detailed procedural protocols in Appendix A3, A4).^{126,127} Design Fidelity. The intervention was designed based on tested Principles of the Transitional Care Model,^{40-42,64} and a tested theoretical framework, the Theory of Symptom Self-Management. Adherence to the theoretical underpinning will be evaluated by the PI through monthly team meetings and the use of intervention guidelines and protocols to include: Efficacy-Enhancing CRF Self-Management Intervention Guidelines (Appendix A6); Nurse Intervener Study Protocol for the IIG, ACG and WCG (Appendix A3, A4); and their respective Daily Diaries (Appendix A2, A7). A monthly team meeting will be held by the PI on use of these guidelines and protocols. Dose Fidelity. Dose of the intervention was designed following the principles of exercise prescription via the ACSM,^{37,80,82,121} AHA,¹²² and ACS.^{79,83} Dose of the intervention for the IIG and WCG is defined in the Exercise Prescription Guidelines (Appendix A1). Likewise, dose of the ACG will be matched to the IIG in frequency, duration, and social interaction. The PI will train the interventionist on dosage and the IIG and WCG Daily Diaries and ACG Telephone Script Logs (Appendix A3) will be evaluated on a monthly basis. Training Fidelity. Initial orientation with standardized training manuals will be used to ensure the required skill level of the interventionists. Quarterly meetings will be led by the PI to maintain knowledge and prevent drift from original protocol. Delivery Fidelity. Weekly interventionists' IIG and WCG logs and ACG logs documenting intervention delivery will be peer reviewed to standardize delivery and ensure protocol adherence. Logs and corresponding audio tapes will be randomly selected on a quarterly basis to ensure adherence with feedback provided regarding performance. Logs and tapes will be used to generate case studies for review in monthly team meetings. Receipt Fidelity. Daily Diaries for the IIG and WCG will be used to assess participant's completion and understanding of the intervention as intended (Appendix A2). The script checklist documenting date, time, and minutes spent by the nurse with the ACG participant will document receipt of the intervention as intended (Appendix A3). Interventionist will review Daily Diaries and recorded prescriptions weekly (via a checklist) with the participant to ensure that the participant was able to understand the prescribed treatment activities. Enactment Fidelity. Interventionists will assess the level of intervention achieved on a weekly basis by the participant through the review of the participant's Daily Diary that documents exercise completed to ensure the participant performed the intervention per prescription.

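### The attention control is described as matched to the exercise arm, but the schedules give 8 nurse contacts with 2 home visits against 6 phone calls, and matched duration is not supported

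*Combined protocol and SAP*

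**What the plan says.** Section 5C1b names three matched properties. It matches the ACG to the "exercise intervention in terms of frequency of visits (1 visit per wk); duration of visit (about 10 mins"), and gives social interaction as the third. Section 5C3, under dose fidelity, says again that the "dose of the ACG will be matched to the IIG in frequency, duration, and social interaction".

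Section 5C2 sets out the IIG contacts. "The nurse will make a phone visit within approximately 24 hrs of post-surgical discharge to screen" readiness, and this step is repeated each day for a participant who is not ready. Then "a home visit will be scheduled to start exercise within approximately 4 days of discharge". That first visit includes connecting the Wii, "setting up Wii FitPlus log on password, teaching exercise intervention, and reinforcing CRF self-management education and exercise safety precautions". A follow-up call comes about 24 hours later. The nurse will then "make a follow-up home visit at approximately the start of wk 2 of exercise", telephone at the start of weeks 3-6, and visit again on request.

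Section 5C2b gives the ACG one call within about 4 days of discharge to start the education. The nurse will then "make phone visits at the start of approximately wks 2-6". Section 5C1b puts these calls at about 10 minutes each. Figure 8 in Section 4.0 marks home visits in the IIG row and none in the ACG row.

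**The concern.** An attention control is there so that a difference from the exercise arm is not simply the result of more contact with a nurse. IIG versus ACG is one of the Aim 1 comparisons, and Section 5B sizes the trial for it within each age group. Both primary outcomes are open to such an effect. The Brief Fatigue Inventory is self-reported, and fatigability (Section 7.0) has a self-rated fatigue score as its numerator.

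The plan itself treats contact as something to control. Section 5C2a gives the wait-list group (WCG) weekly calls partly for that purpose, and Table 1 expects slightly lower fatigue in the ACG than in the WCG. If the arms differ in amount and mode of contact while the protocol calls them matched, a reader will credit the comparison with a control that it lacks.

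**Working it through.** **The plan's own figure.** One visit per week over 6 weeks is 1 × 6 = 6 contacts in each arm.

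**Count from the schedules.** This covers post-discharge contacts by the nurse intervener. Data-collector calls are left out because they are the same in both arms: one about 24 hours after discharge and one at the end of each of weeks 1-6.

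| Period | IIG (5C2) | ACG (5C2b) |
|---|---|---|
| Discharge to end of week 1 | readiness call, home visit, 24-hour call = 3 | starting call = 1 |
| Week 2 | home visit = 1 | call = 1 |
| Weeks 3-6 | calls = 4 | calls = 4 |
| Total | 3 + 1 + 4 = 8 | 1 + 1 + 4 = 6 |
| By phone | 1 + 1 + 4 = 6 | 6 |
| At home | 1 + 1 = 2 | 0 |

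The ACG reproduces the stated 6. The IIG does not: 8 − 6 = 2 more contacts, or 2/6 = 33% more. The 8 is a minimum, because repeat readiness calls and visits on request come on top. Section 5C2b states no on-request visits for the ACG.

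**Where the excess lies.** Up to the end of week 1 the count is 3 against 1. In weeks 2-6 it is 5 against 5, but the IIG contact in week 2 is a home visit.

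**Other ways of counting.**

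- Adding the one hospital visit that each arm receives: 8 + 1 = 9 against 6 + 1 = 7.
- Leaving out the IIG readiness call: 8 − 1 = 7 against 6.
- Leaving out both the readiness call and the 24-hour call: 8 − 2 = 6 against 6. This is the only variant that gives equality, and it is taken up under the objection.

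Home visits are 2 against 0 in every variant.

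**Duration.** The ACG has 6 calls × about 10 minutes = about 60 minutes. No corresponding total can be formed for the IIG, because the text gives no length for its home visits. The first one covers equipment set-up, log-on, exercise teaching, self-management education and safety, so about 10 minutes is doubtful for it. The nurse protocols in Appendices A3 and A4 are not part of the text available here.

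**Social interaction.** Section 5C1b defines this as individual instruction by a nurse. Both arms receive it, so on that definition the statement holds.

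**The case against.** The strongest reply is that the match concerns weekly sessions. On that reading the IIG has a home visit in week 1, a home visit in week 2 and calls in weeks 3-6, which makes 6. The readiness and 24-hour calls are then safety and set-up steps. This fails on the protocol's own terms, because Section 5C2 labels both of these calls phone visits, and visits are the unit that 5C1b says is matched. Even if the reading is granted, the 2-against-0 gap in home visits remains.

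Second, all scheduled staff contact can be counted. With one hospital visit and seven data-collector calls per arm, the totals are 8 + 1 + 7 = 16 against 6 + 1 + 7 = 14, or 14% more. The arithmetic is right, but the matching statement is about the nurse's visits, and the gap in mode is unchanged.

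Third, the effect may be small. In Table 1 the planned ACG advantage over the WCG is 4.5 − 4.3 = 0.2 points below age 65 and 4.2 − 4.0 = 0.2 points at 65 and over. The planned IIG-ACG differences are 4.3 − 2.5 = 1.8 and 4.0 − 2.0 = 2.0. Scaling the 0.2 by contact count gives 0.2 × 2/6 = about 0.07 points. These are planning values, and the scaling ignores mode and length. It is a fair warning against assuming a large bias, but it does not show that there is none.

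Two further points stand. The home-visit difference is disclosed in 5C2 and Figure 8. Home set-up and self-efficacy support are also part of the intervention as defined, so contact spent on them is not all non-specific attention.

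**Conclusion.** The matching statement is wrong as written for frequency, since the scheduled nurse contacts are 8 against 6. It does not hold for mode of contact either, with 2 home visits against 0. For duration it is unsupported. It holds for social interaction as 5C1b defines that term. The count rests on taking every contact that 5C2 and 5C2b schedule after discharge, and it is a minimum for the IIG.

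A reader might go further in three ways that the documents do not support.

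- One is that the IIG receives several times the nurse time of the ACG. That needs an assumed length for the home visits, and none is given.
- Another is that the trial fails in a stated aim to isolate exercise from attention. The protocol never literally says this. It is only implied by the name of the arm and by the matching statement.
- The third is that the primary result will be biased by some known amount. The size of any attention effect cannot be computed from the documents.

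What changes is the interpretation. IIG versus ACG compares the whole exercise and self-management programme, including its extra and in-home nurse contact, with weekly education by phone.

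**What to change.** Reconcile 5C1b and 5C3 with 5C2 and 5C2b. Replace the matching statement with the actual contact schedule of each arm, and state the IIG-ACG contrast in the terms given in the verdict.

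Add date, mode and minutes of every nurse contact to the IIG delivery logs, including repeat readiness calls and visits on request. Section 5C3 already has weekly delivery logs for the IIG but names no minutes field for them, while the ACG script checklist records date, time and minutes. Add mode to the ACG record so that the two can be compared. Report number, mode and minutes of nurse contact by arm beside the primary result.

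The cost is a weaker stated claim for the ACG comparison, a few log fields and one descriptive table. Visits, sample size and analysis model stay as they are. Adding scheduled calls to the ACG is not proposed, because it would leave the home-visit gap in place.

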Justification: To assess the certainty in performing pain-managing behaviors. The PSEPSM was used in the parent NIH, NCI R21 study that led to this current NIH, NCI R01 study. The PSEPSM Instrument is a self-report measure containing 6 items related to the certainty in performing pain-managing behaviors that takes 3 minutes to complete. On an 11-point scale (0-10, 10 = very certain), respondents rate their certainty in performing pain-managing behaviors. For the duration of study participation, measurement will occur with participants pre-surgery, post-surgery, weeks 3, 6, 9, and 12. The PSEPSM has been psychometrically tested developed by the Principal Investigator, [name] [name], based on the Perceived Self-Efficacy for Fatigue Self-Management Tool with internal consistency of 0.92 in the surgical lung cancer population. A copy of the tool is provided in this revision.

Note: In Table 3, a schedule is provided for collection of data. All time points such as Pre- & Post-surgery and Weeks 1 – 12 are collected approximately at this time point.

Table 3. Main Concepts, Variable, Measures, Collection Schedule, and Measurement Objective

Concept	Variable	Measure (# of items)	Schedule	Measurement Description and (Cronbach's alpha):
Patient Characteristics	Physiological	Demographic Questionnaire; Medical Record; Karnofsky Performance Scale.	Pre & Post-Surgery Weeks 1-12	Pre-Surgery: Age; Sex; Race; Co-morbid Conditions; Smoking History; Body Mass Index (BMI); Medications. Post-Sx Treatments (walker, oxygen, adjuvant therapy); Functional Impairment. Post-Surgery: Stage of Cancer; Type of and Extent of Lung Resection; BMI; Medications; Post-Sx Treatments. Weeks 1-12: Medications; Post-Sx Treatment. Wk 6, 12: BMI.
Patient Characteristics	Contextual	Demographic Questionnaire	Pre-Surgery	Education Level; Employment Data; Health Insurance Status; Income Level; and Marital Status.
Symptoms	CRF Severity	Brief Fatigue Inventory (9 items)	Pre & Post-Surgery Weeks 1-12	Severity of CRF and impact of CRF on daily living (.82-.97).
Symptoms	Other Symptom Severity	M.D. Anderson Symptom Inventory Lung Cancer Module (22 items)	Pre & Post-Surgery Weeks 1-12	Severity of pain, nausea, disturbed sleep, distress, dyspnea, difficulty remembering, decreased appetite, drowsiness, dry mouth, fatigue, sadness, numbness/tingling, vomiting, sore throat, cough, constipation and impact on daily living (.82-.94).

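### Section 5C2a does not require the wait-list arm's week-6 outcomes to be collected before the exercise nurse's week-6 contact, so some usual-care end points may be measured after it

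*Combined protocol and SAP*

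**What the plan says.** Section 5C2a describes two contacts with the WCG around week 6.

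- **Outcome call.** "Research staff will perform phone visits using protocol in Appendix A8 at the approximate end of wks 1-6 to control for staff interaction". This call yields the week-6 BFI and the other phone questionnaires.
- **Readiness call.** "During wk 6, an exercise nurse intervener will make a phone visit to screen" readiness, in the way described for the IIG. Once the participant is ready, a home visit is arranged within about 3 days.

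The IIG procedure in Section 5C2 defines the screen. A participant is ready if "usual level of severity for key symptoms of pain, nausea, and dyspnea are rated" 4 or less on a 0-10 scale. If one of them is above 4, the "nurse will intervene and contact" the surgeon's office, and "The nurse will repeat this step each day until participant is ready to start exercising". The first home visit sets up the Wii, teaches the exercise and reinforces fatigue self-management education.

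Other parts of the protocol bear on the timing:

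- The note before Table 3 says "All time points such as Pre- & Post-surgery and Weeks 1 – 12 are collected approximately at this time point".
- Figure 8 lists, for the WCG around week 6, the six-minute walk test (6MWT), then a home visit, then data collection. The column layout may have been disturbed when the PDF was read.
- Section 5C1a defines WCG weeks 1-6 as standard medical care, and Section 7.0 (Aim 2) starts the WCG intervention at the beginning of week 7.
- Section 10.0 places the Aim 1 primary analysis at about 6 weeks.

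**The concern.** The week-6 WCG value is the usual-care end point for Aim 1. Section 5C2a assigns the weekly calls to research staff in order to control for staff interaction. A call from the exercise nurse who acts on symptoms, or a visit that teaches the exercise, lies outside that control and outside the definition of usual care.

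The contact can also reach the outcomes. Pain, nausea and dyspnea are items of the M.D. Anderson Symptom Inventory, collected weekly. Pain is measured again by the Brief Pain Inventory at week 6, and the protocol's reason for adding that tool is that pain correlates highly with cancer-related fatigue. Relief of a screened symptom before the outcome call could therefore lower the WCG fatigue score and shrink the IIG-WCG difference. Anticipation of starting exercise could move self-reports either way. Because the order is not fixed, exposure before measurement may also vary between participants.

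**Working it through.** **1. Order of contacts.** The readiness call may fall on any day of week 6, and the outcome call falls at about the end of week 6. Call first is the more natural reading. Outcomes first also fits both sentences, because the outcome date is approximate. No available section settles it. The home visit has only an upper limit of about 3 days after readiness and no lower limit tied to the outcomes. A participant screened early in week 6 could therefore be visited before the week-6 BFI. Figure 8, as read, also places the home visit before data collection, which has to be reconciled with a start at week 7.

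**2. The plan's own power.** Inputs from Section 5B:

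- SD 2.0 and two-sided alpha 0.05
- 20 per arm aged under 65, and 40 per arm aged 65 and over
- Table 1 differences, WCG minus IIG: 4.5 − 2.5 = 2.0 under 65, and 4.2 − 2.0 = 2.2 at 65 and over

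Formula (normal approximation): power ≈ Φ(d / (SD × √(2/n)) − 1.96).

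- Under 65: 2.0 × √(2/20) = 0.632; 2.0/0.632 = 3.16; Φ(1.20) = 0.885. Table 2 states 0.88.
- 65 and over: 2.0 × √(2/40) = 0.447; 2.2/0.447 = 4.92; Φ(2.96) = 0.998. Table 2 states above 0.99.

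Both figures reproduce.

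**3. Sensitivity.** The documents give neither the share of the WCG rated above 4 nor the effect of the contact on the BFI. The shift in the WCG week-6 mean is therefore an assumption, shown over a range:

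| Assumed fall in WCG mean BFI | Difference, <65 | Power, <65 | Difference, 65+ | Power, 65+ |
|---|---|---|---|---|
| 0 | 2.00 | 0.885 | 2.20 | 0.998 |
| 0.1 | 1.90 | 0.852 | 2.10 | 0.997 |
| 0.25 | 1.75 | 0.790 | 1.95 | 0.992 |
| 0.5 | 1.50 | 0.660 | 1.70 | 0.967 |

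The arm-level shift is the share affected times the change in those affected. Half the arm improving by 0.5 points gives 0.5 × 0.5 = 0.25. Half the arm improving by 1 point gives 0.5 × 1 = 0.5, so the last row needs a substantial effect in many participants.

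**The case against.** The strongest reply is that the order is inferred. A readiness call made in the last days of week 6, after data collection, satisfies every sentence. The sequence may also be set in Appendix A8 or in the nurse protocols (Appendices A3 and A4), which are not in the available text. This stands, and it limits the point to an order that the plan leaves open.

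A reader might go further and infer that the whole WCG is already under nurse intervention when its end point is measured. The documents do not support that. For a participant who rates all three symptoms at 4 or less, the call is only a screen, and exercise is stated to begin in week 7. Figure 8 lists the 6MWT before the home visit, so fatigability looks less exposed to that visit than the phone outcomes, although the figure does not show the screening call.

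A reader might also try to size the effect from the pilot usual-care symptom severity at week 6, mean 3.8 (SD 1.5). A normal curve puts 45% above 4. But that mean covers 15 other symptoms, not the three screened. The rule is triggered by any one of the three, which under independence would give 1 − 0.553³ = 83%. A single whole-number rating, cut at 4.5, would give 32%. The share cannot be derived from these data, and no BFI effect can be sourced.

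The contact is also not wholly new. The WCG already has a nurse visit in hospital and weekly staff calls, and Section 10.0 refers participants with unmanaged symptoms to their provider. This reduces the added exposure. It does not explain why the end point should follow the exercise nurse's contact.

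**Conclusion.** The point holds in a limited form. As written, the plan allows the Aim 1 usual-care end point to be measured after exercise-nurse contact in some WCG participants. The exposure is mainly to the BFI and phone questionnaires. The plan does not state that this order will occur, or that it applies to the whole arm.

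The size is unknown. Over assumed shifts of 0.1 to 0.5 BFI points, IIG versus WCG power under 65 falls from 0.88 to between about 0.85 and 0.66, while power at 65 and over stays at about 0.97 or higher. These figures rest on the plan's SD, differences and sample sizes, and on the assumed shift. The likely direction is towards no difference, which is conservative for Hypothesis 1. IIG versus attention control is unaffected. This is a cheap improvement to the plan and does not threaten the trial's main conclusion.

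**What to change.** State in Section 5C2a that the WCG week-6 BFI, questionnaires and 6MWT are completed before the exercise nurse's readiness call and home visit. Reconcile Figure 8 and the week-7 start in Section 7.0 with that order, and check the appendices for consistency. Record the date of each outcome, the readiness call and the home visit. The content of the screen and its criteria need not change.

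For participants already past week 6, use the available dates in a sensitivity analysis that excludes WCG participants contacted before measurement. That exclusion depends on events after randomization, so it should support the intent-to-treat result and not replace it.

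The cost is small but not zero. Screening repeats daily until the participant is ready, and the home visit follows within about 3 days. Holding the call until the outcomes are complete may delay the WCG exercise start by a few days and slightly shift the weeks 7-12 window used for Aim 2. The recorded dates would show by how much.
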